4.8. Interim Analyses

The details for the interim analyses and Data Monitoring Committee will be provided in the Data Monitoring Committee Charter.

4.8.1. *Unblinding Plan*

Details of the blinding and unblinding are provided in the Blinding and Unblinding Plan document for Master Protocol GPIF.

4.9. Changes to Protocol-Planned Analyses

Refer to [Table GPIF.1.1](#).

5. Sample Size Determination

Approximately 206 participants per ISA will be randomly assigned to either tirzepatide or placebo in a 1:1 ratio (approximately 103 participants per treatment arm), and the statistical power will be evaluated for the primary efficacy endpoint and key secondary combination PRO endpoint at a 2-sided significance level of 0.05. This sample size will provide the following:

- at least 90% power to demonstrate superiority of tirzepatide at the MTD (10 mg or 15 mg) to placebo for the mean percent change from baseline in AHI, assuming 50% improvement, with a common standard deviation of 50% and a dropout rate of 25%, and
- at least 90% power to demonstrate superiority of tirzepatide at the MTD (10 mg or 15 mg) to placebo for the hierarchical combination PRO endpoint using the Finkelstein-Schoenfeld method (Finkelstein and Schoenfeld 1999), with a dropout rate of 25%.

An upper limit of approximately 70% enrollment of male participants will be used to ensure a sufficiently large sample of female participants.

6. Supporting Documentation

6.1. Appendix 1: Clinical Trial Registry Analyses

Additional analyses will be performed for the purpose of fulfilling the Clinical Trial Registry requirements.

Analyses provided for the Clinical Trial Registry requirements include the following:

- Summary of AEs, provided as a dataset which will be converted to an XML file. Both SAEs and 'Other' non-SAEs are summarized: by treatment group, by MedDRA PT.
 - An AE is considered 'Serious' whether or not it is a TEAE.
 - An AE is considered in the 'Other' category if it is both a TEAE and is not serious. For each SAE and 'Other' AE, for each term and treatment group, the following are provided:
 - the number of participants at risk of an event
 - the number of participants who experienced each event term, and
 - the number of events experienced.
- For each SAE, these additional terms are provided for EudraCT:
 - the total number of occurrences causally related to treatment
 - the total number of deaths, and
 - the total number of deaths causally related to treatment.
- Consistent with www.ClinicalTrials.gov requirements, 'Other' AEs that occur in fewer than 5% of participants/subjects in every treatment group may be excluded.
- AE reporting is consistent with other document disclosures for example, the CSR, manuscripts, and so forth.

Demographic table including the following age ranges required by EudraCT: adults (18 to 64 years), (65 to 85 years), and (85 years and over).

6.2. Appendix 2: Search Criteria for Special Safety Topics

Arrhythmias and cardiac conduction disorders

Treatment-emergent arrhythmias, arrhythmias and cardiac conduction disorders will be considered an AESI. The cardiovascular events will include clinically relevant rhythm and conduction disorders. The treatment-emergent arrhythmias and cardiac conduction disorders events will be included using the MedDRA PT contained in any of the following SMQs:

- 1) Arrhythmias:
 - a. For symptoms: *Arrhythmia related investigations, signs and symptoms* SMQ (20000051), narrow and broad terms

- b. For supraventricular arrhythmias: In *Cardiac arrhythmia* SMQ, under tachyarrhythmia sub SMQ
 - i. *Supraventricular tachyarrhythmia* SMQ (20000057), broad and narrow terms
 - ii. *Tachyarrhythmia terms, nonspecific* SMQ (20000164), narrow terms only; and
 - iii. *Ventricular tachyarrhythmia* SMQ (20000058), narrow terms only.
- 2) Cardiac conduction disorders
 - a. *Conduction defects* SMQ (20000056), narrow terms only; and
 - b. *Cardiac conduction disorders* HLT (10000032), all PTs.

Hepatic TEAEs

Treatment-emergent potentially drug-related hepatic disorders will be summarized by treatment using the MedDRA PTs contained in any of the following SMQs:

- broad and narrow terms in the *Liver related investigations, signs and symptoms* SMQ (20000008)
- broad and narrow terms in the *Cholestasis and jaundice of hepatic origin* SMQ (20000009)
- broad and narrow terms in the *Hepatitis non-infections* SMQ (20000010)
- broad and narrow terms in the *Hepatic failure, fibrosis and cirrhosis and other liver damage* SMQ (20000013), and
- narrow terms in the *Liver-related coagulation and bleeding disturbances* SMQ (20000015).

Acute gallbladder disease

All events of TEAE biliary colic, cholecystitis, or other suspected events related to gallbladder disease will be summarized by treatment groups by PT with decreasing frequency under the following SMQs:

- narrow PTs in *Gallbladder related disorders* SMQ (20000124)
- narrow PTs in *Biliary tract disorders* SMQ (20000125), and
- narrow PTs in *Gallstone related disorders* SMQ (20000127).

Major depressive disorder/suicidal ideation

AEs will be searched using MedDRA PTs from SMQs narrow scope: 20000037 (*Suicide/self-injury*) and 20000167 (*Depression [excl suicide and self injury]*).

C-cell hyperplasia and thyroid malignancies

Thyroid malignancies and C-cell hyperplasia will be identified using MedDRA HLT for *Thyroid neoplasms* and PT for *Thyroid C-cell hyperplasia*.

Hypersensitivity reactions

Analyses are based on the following:

- narrow and algorithm terms in *Anaphylactic reaction* SMQ (20000021)
- narrow terms in *Angioedema* SMQ (20000024)
- narrow terms in *Severe cutaneous adverse reactions* SMQ (20000020), and
- narrow terms in *Hypersensitivity* SMQ (20000214).

For the Anaphylactic reaction SMQ, each term is classified by scope (narrow, broad) and by category (A, B, C, and D). All narrow terms are category A, and all broad terms are category B, C, or D. In addition to the usual narrow and broad searches, the SMQ defines an algorithm to further refine the cases of interest. For Time Period A analysis, the *Anaphylactic reaction* SMQ algorithm will be included. The algorithm is based upon events that occur within Time Period A. The counts and percentages of participants who experienced a TEAE for the following will be analyzed for each of the 2 time periods:

- any narrow term from any 1 of the 4 SMQs indicated above (that is, combined search across narrow of all 4 SMQs), and
- any narrow scope term within each SMQ, separately (that is, narrow SMQ search). For Time Period A analysis, any term from *Anaphylactic reaction* SMQ algorithm.

Injection site reactions

The ISR AE will be identified using the MedDRA PT in any of the following:

- HLT of *Injection site reaction*
- HLT of *Administration site reaction*, and
- HLT of *Infusion site reactions*.

Pancreatitis events

Determination of investigator-reported events will be through the *Acute pancreatitis* MedDRA SMQ (20000022, narrow scope) and a *Chronic pancreatitis* PT search of the AE database, while adjudication-confirmed pancreatitis is found from adjudication forms.

6.3. Appendix 3: Magnetic Resonance Imaging Addendum

This section is applicable to the participants who are enrolled in the MRI addendum.

This addendum applies to a subset of participants (approximately 58 participants) enrolled in ISA1. MRIs for the assessment of fat dispositions will be collected at baseline and Week 52. The MRI at baseline needs to be completed prior to Visit 2 or within 7 days after Visit 2. The MRI at Week 52 may be scheduled for any day \pm 14 days.

MRI analyses will be guided by the treatment policy strategy and conducted among all participants who are enrolled in the addendum, received at least 1 dose of study drug, and have baseline and at least 1 postbaseline MRI measurement. No imputation will be performed for

missing data. The participant's demographics and baseline characteristics for the MRI addendum will be summarized.

| Objectives | Endpoints | Analytical Approaches |
|---|--|---|
| Compare the effect of once weekly tirzepatide at MTD versus placebo on the changes of soft tissues volumes, fat volumes and fat content (%) in upper airway structures and in the abdomen in participants with OSA and obesity. | 
Changes of absolute soft tissue volume, fat volume and fat content (%) of the following:
 
 • Tongue • Soft palate • Pterygoid muscle • Lateral pharyngeal walls • Neck and submandibular area • Total, visceral and subcutaneous abdominal fat | 
Change from baseline to Week 52 for each parameter will be compared between treatment arms using an ANCOVA approach. The model will include treatment, the stratification factors of gender, and baseline AHI (not severe/severe), and the baseline value for the parameter. Summary statistics for MRI parameters at baseline and at Week 52 will be provided. The treatment comparison at baseline will be performed using an ANOVA model.
 |
| Explore correlation of changes of soft tissue volumes, fat volumes, and fat content (%) in upper airway structures and in the abdomen with changes of AHI. | Correlations between the change in absolute soft tissue volume, fat volume, and fat content (%) for the structures listed above and the % change in AHI. | Spearman correlations between the change from baseline for each of the MRI endpoints and the % change in AHI will be calculated. |

Abbreviations: AHI = Apnea-Hypopnea Index; ANCOVA = analysis of covariance; ANOVA = analysis of variance; MRI = magnetic resonance imaging; MTD = maximum tolerated dose; OSA = obstructive sleep apnea.

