4.1.2. Handling of Dropouts or Missing Data

For the primary and key secondary efficacy endpoint analyses aligned to the treatment regimen estimand and subject to Type 1 error rate control, missing data will be imputed based on the reason for the missing values, as described in [Table GPIF.4.2](#). For analyses aligned to the “efficacy” estimand, missing data will be considered missing at random and hence no explicit imputation will be performed.

For exploratory endpoints and safety analyses, missing values will not be explicitly imputed unless specified otherwise.

For analyses aligned to the treatment regimen estimand, the statistical inference over multiple imputations will be guided by the method proposed by Rubin (1987). The missing values will be handled as follows:

Table GPIF.4.2. Imputation Approaches to Handle Missing/Invalid Data for Treatment Regimen Estimand

| Missing/Invalid Data | Strategy to Handle Missing/Invalid Data | Assumptions for Missing Values | Methods to Handle Missing Values |
|--|---|--------------------------------|--|
| Data missing at baseline, invalid data collected or missing data after treatment DC due to the COVID-19 pandemic (after other reasons for missing data are ruled out), technical issues (that is, sensor error on PSG) leading to invalid measurements ascertained while on treatment, or missing data after study DC due to inadvertent enrollment. | Hypothetical | MAR | Multiple imputation assuming MAR |
| Missing data due to any other reason (for example, study DC due to any reason other than COVID-19 or inadvertent enrollment). | Treatment policy | MNAR | Retrieved dropout imputation ^a . If there are not enough retrieved dropouts to provide a reliable imputation model, placebo-based multiple imputation will be used. |

Abbreviations: COVID-19 = coronavirus disease-2019; DC = discontinuation; MAR = missing at random;

MNAR = missing not at random; PSG = polysomnography; SBP = systolic blood pressure.

^a Retrieved dropout imputation utilizes observed data from participants in the same treatment group who had outcome measures at Week 52 (or Week 48 for SBP) after early DC of study drug to impute the missing value.

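### SAP 6.3 labels the MRI analyses treatment policy, but its observed-case ANCOVA takes missing Week 52 scans as missing at random, unlike the SAP's handling of study dropouts under that strategy

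*SAP*

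**What the plan says.** SAP 6.3 describes a small sub-study: "This addendum applies to a subset of participants (approximately 58 participants) enrolled in ISA1". On timing, "MRIs for the assessment of fat dispositions will be collected at baseline and Week 52", so only one postbaseline scan is scheduled. On strategy and population, "MRI analyses will be guided by the treatment policy strategy and conducted among all participants who are enrolled in the addendum"; these participants must also have had at least one dose and "have baseline and at least 1 postbaseline MRI measurement. No imputation will be performed for" missing data. On the model, "Change from baseline to Week 52 for each parameter will be compared between treatment arms using an ANCOVA approach", adjusting for gender, AHI stratum and the parameter's baseline value. Nothing in the section requires a participant to be on drug when scanned. The version history shows that the no-imputation sentence was added in version 3 as a clarification.

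Three other SAP sections bear on this:

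- **4.1.2.** The second row of Table GPIF.4.2 covers "Missing data due to any other reason (for example, study DC due to any reason other than COVID-19 or inadvertent enrollment"). It pairs the treatment policy strategy with an MNAR assumption. The method is retrieved-dropout imputation, with placebo-based multiple imputation if retrieved dropouts are too few. The table is scoped to primary and key secondary endpoints under the treatment regimen estimand. Exploratory and safety endpoints are not imputed unless the SAP says so.
- **4.4.3.1.** For the hierarchical PROMIS endpoint, which carries no Type 1 error control, missing Week 52 values under a treatment policy estimand are imputed by the rules of 4.1.2.
- **4.5.** Exploratory efficacy analyses follow the efficacy estimand unless otherwise stated.

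**The concern.** A treatment policy comparison in dosed addendum participants asks what the MRI difference is whatever happens to treatment. To answer it for everyone dosed, the analysis has to take some position on those with no Week 52 scan. Excluding them without imputation takes a position silently: given arm, gender, AHI stratum and baseline value, they would have changed as much as those who were scanned. Elsewhere, under the same label, the SAP takes the opposite view of participants who leave the study.

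The direction of error is predictable if leavers have also stopped drug and lose effect: the tongue, palate, pharyngeal and abdominal differences would be too large for the stated question. The MRI results are likely to be read beside the treatment regimen AHI result, as the mechanism behind it, although the two handle the same leavers differently. SAP 6.3 states neither the assumption nor a sensitivity analysis, and does not commit to reporting missing scans by arm.

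**Working it through.** **1. The plan's own figure.** The MRI addendum has no power statement and no dropout rate. The only calculation that carries one is SAP Section 5, for a whole ISA: "tirzepatide or placebo in a 1:1 ratio (approximately 103 participants per treatment arm"), "assuming 50% improvement, with a common standard deviation of 50% and a dropout rate of 25" per cent, with at least 90% power at two-sided 0.05. Check: 103 × 0.75 = 77.25, so 77 per arm. A two-sample comparison with difference 50 and SD 50 then has 99.99% power. For 90% power it needs 22 per arm, and 22 / 0.75 = 29.3, so 30 with dropout. The statement holds as a lower bound. It concerns percent change in AHI, and only the 25% is borrowed here. Applied to the addendum, 58 × 0.75 = 43.5, so about 43 or 44 would be analysed.

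**2. Who is in and who is out.** With one scheduled postbaseline scan, having at least one means having the Week 52 MRI.

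- Scanned, on drug: included.
- Scanned, off drug or (in ISA1) after starting PAP: included, as treatment policy requires.
- Not scanned: excluded, with no intermediate scan to borrow from.

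Only the third group separates the analysis from its label.

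**3. Size of the gap.** Let D be the treatment difference among those scanned, m the share of tirzepatide participants not scanned, and k the share of D that they would show. Assume unscanned placebo participants resemble scanned ones. Then:

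- treatment-policy effect = D × [(1 − m) + m × k]
- overstatement = 1 / [(1 − m) + m × k] − 1

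Here k = 0 corresponds to the SAP's placebo-based fallback, and k = 1 to MAR.

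| m | k = 0 | k = 0.5 | k = 1 |
|---|---|---|---|
| 10% | 1/0.900 − 1 = 11.1% | 1/0.950 − 1 = 5.3% | 0% |
| 12.5% | 1/0.875 − 1 = 14.3% | 1/0.9375 − 1 = 6.7% | 0% |
| 25% | 1/0.750 − 1 = 33.3% | 1/0.875 − 1 = 14.3% | 0% |
| 30% | 1/0.700 − 1 = 42.9% | 1/0.850 − 1 = 17.6% | 0% |

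The 12.5% row is the case where half of a 25% loss returns for the scan.

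**4. Simulation check.** Settings were 29 per arm (an even split of 58, which the SAP does not state), 25% missing in each arm, k = 0, a true difference of 1 SD among those scanned, and 20,000 replicates. The mean difference was −0.748 in all participants and −1.000 in those scanned. The ratio is 1.337, against 1.333 from the formula.

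**5. Unequal loss.** With k = 0 the result depends only on tirzepatide loss. Holding the overall loss at 25%, a tirzepatide/placebo split of 20%/30% gives 25.0%, 30%/20% gives 42.9%, and 35%/15% gives 53.8%.

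**The case against.** The strongest reply is that not imputing is the SAP's default here. Table GPIF.4.2 is scoped to primary and key secondary endpoints, MRI is neither, and 4.1.2 leaves exploratory endpoints unimputed unless stated otherwise. That stands as a statement of scope: the addendum breaks no rule in the table. It does not settle the matter. Under 4.5 the default estimand for exploratory efficacy is the efficacy estimand, for which the SAP itself assumes MAR, so not imputing is coherent there. SAP 6.3 keeps the no-imputation default but changes the estimand. And 4.4.3.1 shows the SAP imputing under a treatment policy label for an endpoint outside Type 1 error control.

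Second, a reader might infer that this is an on-treatment or treatment-completer analysis. The documents do not support that. The on-treatment set (EAS, SAP Section 3) drops data from more than 7 days after the last dose and, in ISA1, data after PAP starts; the MRI analysis drops neither. Protocol 7.1 keeps participants who stop drug in the study and encourages those who decline further visits to return for Visit 11.

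Third, a reader might take one third as the likely bias or its ceiling. It is neither. The 25% is a planning rate for the main ISAs, and Protocol 7.2 expects few withdrawals from the study. Some scans may be missing for technical reasons, or after study discontinuation for inadvertent enrolment, which Table GPIF.4.2 itself treats as MAR. Unequal loss, on the other hand, can push the figure above a third.

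Finally, making imputation the main analysis is debatable. At 25% loss, about 14 or 15 scans (58 × 0.25 = 14.5) would be imputed from about 22 scanned placebo participants (29 × 0.75 = 21.75, assuming an even split), for many parameters. That argues for a sensitivity analysis rather than a replacement.

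**Conclusion.** The mismatch between label and missing-data assumption is real but limited. Treatment discontinuation is handled as the label says. What is unaddressed is the group never scanned at Week 52, implicitly MAR in SAP 6.3 but, where they have left the study, MNAR under the same strategy in Table GPIF.4.2.

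If those missing respond like placebo, the MRI difference overstates the treatment-policy effect by about 11% at 10% missing in the tirzepatide arm and 33% at 25%. If they keep half the effect, it is about 5% and 14%. It is zero under MAR, and above 33% if tirzepatide loss exceeds 25% and those missing respond like placebo. These scenarios rest on an assumed missing rate, since none is given for the addendum, and on unscanned placebo participants resembling scanned ones. Only the interpretation of the MRI results is affected; the primary and key secondary conclusions are not. This is a cheap improvement to the plan.

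**What to change.** In SAP 6.3:

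1. Keep the current ANCOVA, and describe it as an observed-case analysis under MAR in participants with a Week 52 MRI.
2. Report the number of missing Week 52 MRIs by arm and reason.
3. Add one prespecified sensitivity analysis: placebo-based multiple imputation for all dosed addendum participants with a baseline MRI, with MAR imputation where the reason falls in the first row of Table GPIF.4.2. With about 58 participants, retrieved dropouts are unlikely to support an imputation model.

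If the sponsor does not want the sensitivity analysis, remove the reference to the treatment policy strategy and limit the conclusion to participants with a Week 52 MRI.

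The cost is a few lines of SAP text and a little more programming, with no new data. The sensitivity estimate will be somewhat smaller and less precise than the main one.

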6.4. Appendix 4: Statistical Analysis for China

Analyses will be performed for the following subpopulations:

- participants enrolled in East Asian countries/regions (China, Japan), and
- participants enrolled in China.

The analysis methods for the above-mentioned subgroups will be similar to those described for the main part of this SAP. If there is not a sufficient number of participants in the subpopulation, summary statistics will be provided.

The analyses to be included will be documented in a separate list of analyses which should include disposition, demographics, and selected efficacy and safety endpoints.

6.5. Appendix 5: Statistical Analysis for Japan

Analyses will be performed for the following subpopulations:

- participants enrolled in Japan, and
- the JASSO subpopulation, participants who meet the criteria of the JASSO (not limited to the participants enrolled in Japan).

The JASSO subpopulation analysis will be performed according to the criteria of both BMI and obesity-related health problems according to the treatment flow of obesity disease in the obesity disease treatment guideline (JASSO 2022). The JASSO guideline states that drug treatment in

participants with obesity disease should follow with a BMI above or equal to 25 kg/m² (in this trial, BMI enrollment was started from 27 kg/m²), and at least 2 obesity-related health problems, or a BMI above or equal to 35 kg/m² and at least 1 obesity-related health problem out of the 11 obesity-related health problems, including OSAS, listed below. The overall population and participants with obesity disease according to the JASSO guideline will be compared.

The analysis methods for the above-mentioned subgroups will be similar to those described for the main part of this SAP. If there is not a sufficient number of participants in the subpopulation, summary statistics will be provided.

As a low number of participants were enrolled from Japan, combined analyses with both ISAs may be conducted to explore a future line extension for the OSAS indication in Japan.

The analyses to be included will be documented in a separate list of analyses which should include disposition, demographics, and selected efficacy and safety endpoints.

Eleven obesity-related health problems

The JASSO guideline defines 11 health problems for the diagnosis of “Obesity Disease” in subjects who need weight reduction for a medical reason. Data collected by a specific CRF will be used to specify the obesity-related health problems for each participant. The list of the 11 health problems are:

- 1) Glucose intolerance disorder (type 2 diabetes, impaired glucose tolerance [IGT], and so on)
- 2) Dyslipidemia
- 3) Hypertension
- 4) Hyperuricemia and Gout
- 5) Cardiovascular disease, myocardial infarction and Angina
- 6) Cerebral infarction and transient ischemic attack (TIA)
- 7) Non-alcoholic fatty liver disease (NAFLD)
- 8) Menstruation disorder and infertility
- 9) Obstructive sleep apnea syndrome (OSAS) and obesity-hypoventilation syndrome
- 10) Motor dysfunction: arthritis/osteoarthritis (knee, hip joint, supine, and so on), and
